Rationale for PPJ. *Why combine daily life review (including gratitude interventions) with planning for the future (activity scheduling) in a daily exercise?* Gratitude interventions and activity scheduling should reinforce and extend each other’s impact. A positive correlation between higher levels of gratitude and greater behavioral activity have been reported.^{29,30} This association may be causal: in previous research, gratitude has been shown to improve affect^{17,31} which has been shown to encourage more frequent and more diverse types of activity.³² Therefore, gratitude intervention should encourage positive, abstinent behavior. Conversely, activity scheduling will enhance gratitude by guiding individuals to shape

their own positive experiences rather than to passively notice them.

Positive behaviors will produce content to populate the next day's gratitude inventory.

3. The next phase of this study will add to the existing knowledge base because we will collect more information about PPJ's feasibility, acceptability and impact with a larger sample size. Our development study included only women; this phase of the study will include women and men. We will also have a control group in this next phase of the study. We will also modify the protocol so we can conduct the study on Zoom to comply with shelter-in-place orders and COVID19 best practices Study Endpoints/Events/Outcomes

- 3.1. Primary Endpoint/Event/Outcome: The primary outcome is empirical data on the feasibility and acceptability of PPJ. We will also assess rates of substance use and treatment retention as primary outcomes.
- 3.2. Secondary Endpoint(s)/Event(s)/Outcome(s): These include hypothesized mediators of the effect of the intervention on outcomes. These include: mood, satisfaction with life, commitment to sobriety, alcohol and drug craving, anxiety, and depression. For a complete list, see the measures section 5.2.

4. Study Intervention(s)/Interaction(s)

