Secondary measures: outcomes and mediators. We will compare rates of treatment retention and recurrence of substance use to the general rates reported by NUWAY. We will also examine pre-post treatment means and standard deviations of hypothesized mediators (affect, satisfaction with recovery, individual items theoretically related to PPJ) to determine if change is in the expected direction. We will also study these constructs to determine if there is reasonable variability in the data we collect or if floor or ceiling effects are present. We may also use single-subject designs⁵⁶ to depict change over time in key constructs by study participant. Qualitative data will be thematically analyzed using the techniques recommended by Braun and Clarke.¹³ Here, the researcher examines transcripts of texts and identifies key themes and how themes relate to one another. These data will inform intervention development and study implementation procedures.

Data analytic techniques to compare treatment and control groups. While this pilot study will not be adequately powered to detect significant effects between treatment and control groups, we will compare differences between the treatment and control groups at baseline and over time using either t-tests or multi-level modeling. T-tests will reveal significant differences between groups and multi-level modeling will show whether rate of change is significantly different between groups.

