17.2. Power Analysis: Preliminary data from existing behavioral activation (BA) research was used to determine power for the original proposal with N=76. For the outcome of abstinence (yes/no), previous work found outcomes for this variable of 41.5% for the BA group and 24.8% in the control group.¹⁴ For a 1-tailed test with $p < .10$, our power to detect a significant effect for abstinence (yes/no) in the proposed study would be .61 (for a 2-tailed test with $p < .05$, power would be .34). For the outcome of treatment retention (yes/no), previous work showed 96.6% for the BA group and 75.9% in the control group.¹⁶ For a 1-tailed test with $p < .10$, our power to detect a significant effect for treatment retention (yes/no) in the current study would be 94% (for a 2-tailed test with $p < .05$, power would be .82). Therefore, we should be adequately powered to detect statistically significant differences for the outcome of treatment retention in the current study using a 2-tailed test. R was used to conduct these power analyses.⁶¹

17.3. Statistical Analysis: This pilot study will not be adequately powered to detect an effect. Still we will compare the treatment and control groups using t tests and multi-level models to determine differences in means and in slopes between the groups, respectively. Descriptive statistics of the quantitative measures will be used to conduct power analyses and sample size calculations for a larger controlled trial. Also, multi-level analyses will

be conducted to determine significant change over time in factors of interest. We will also be able to examine whether change over time varied by certain subgroups (e.g., those with lower versus higher levels of the factor of interest at baseline).

17.4. Data Integrity: The use of Qualtrics to collect survey data will improve data accuracy because this allows us to avoid keystroke and other errors involved with manual data entry from written questionnaires. We will scrutinize the data produced by Qualtrics to ensure its integrity; whether values are within scale ranges and whether missing data is coded correctly. We will carefully examine and clean the data to ensure accuracy. For standardized instruments, we will be very careful to follow the directions for summing or taking the mean of scale items and reverse code any items as per the instructions.

18. Confidentiality

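### Continuous mediators: the arm comparisons leave the baseline score unused, which costs precision, and the optional lower-versus-higher-baseline look names no arm, which exposes it to regression to the mean

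*Combined protocol and SAP*

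**What the plan says.** - Section 3.2 makes the hypothesized mediators secondary outcomes, among them "mood, satisfaction with life, commitment to sobriety, alcohol and drug craving, anxiety, and depression".
- Section 5.2, in the paragraph on comparing the two arms: "we will compare differences between the treatment and control groups at baseline and over time using either t-tests or multi-level modeling". It adds that "multi-level modeling will show whether rate of change is significantly different between groups".
- Section 17.3: "Still we will compare the treatment and control groups using t tests and multi-level models to determine differences in means and in slopes". Neither section names a baseline covariate, a common baseline mean, a time point for the t-test or a term for PPJ group.
- Table 2 gives most mediators a baseline score. The single-item commitment question is an exception, although the full commitment scale has one. Anxiety/depression and flourishing are scheduled on four occasions. Affect, craving, self-efficacy and satisfaction with life are also asked at every upload, which the table of study activities by arm puts at 3-4 times a week in Phase 1 and daily in Phase 2.
- Section 17.3 then says that multi-level analyses will "be conducted to determine significant change over time in factors of interest", and continues: "We will also be able to examine whether change over time varied by certain subgroups (e.g., those with lower versus higher levels" of the measure at baseline. Neither sentence names an arm.
- Only the treatment arm is taught in groups (section 5.2). Section 8.1 recruits batches of 10-20 to fill one or two treatment groups together with corresponding controls.
- Sections 5.2 and 17.3 both say that the pilot is not adequately powered for arm differences. Section 17.3 also says: "Descriptive statistics of the quantitative measures will be used to conduct power analyses and sample size calculations for a larger controlled trial".

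**The concern.** Randomization follows the baseline battery, so the baseline score is a legitimate covariate that costs nothing further to collect. A t-test on post scores ignores it. A t-test on change scores, or a slope model with a separate baseline mean in each arm, uses it inefficiently. The arm estimates are then less precise than the collected data allow, in a trial that is already small.

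The baseline look carries a different risk. People selected for a low first score tend to score higher next time, and people selected for a high score tend to score lower, with or without treatment. If the look is run on everyone together, or on the PPJ arm alone, this can be misread as PPJ helping those who start low. Such a reading could shape the larger trial.

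**Working it through.** **The plan's own figures.** Section 17.2 "was used to determine power for the original proposal with N=76" (38 per arm if 1:1). With h = 2·asin√p1 − 2·asin√p2 and power = Φ(h·√(38/2) − z):

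- Abstinence, 41.5% v 24.8%: h = 0.357, power 0.609 (one-sided .10) and 0.344 (two-sided .05). Stated: .61 and .34.
- Retention, 96.6% v 75.9%: h = 0.655, power 0.942 and 0.815. Stated: .94 and .82.

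All four reproduce, but they concern the yes/no outcomes. No figure is given for any continuous mediator.

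**Assumed inputs.** Correlation r = .5 to .7; 50 per arm (about 100 consented, section 11.1, if 1:1 and all analysed) or 38 per arm. None of the r values is in the documents.

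**Precision of a comparison of means.** The variance factor relative to a post-score t-test is 1 for post scores, 2(1−r) for change scores and 1−r² when adjusted.

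- Adjusted against post, 1−r²: 0.75, 0.64, 0.51 at r = .5, .6, .7, a cut of 25-49%.
- Adjusted against change, (1+r)/2: 0.75, 0.80, 0.85, a cut of 15-25%.

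Difference detectable with 80% power, two-sided 5%, in SD, at r = .5/.6/.7:

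| Per arm | Post | Change | Adjusted |
|---|---|---|---|
| 50 | 0.566 | 0.566/0.506/0.438 | 0.490/0.453/0.404 |
| 38 | 0.651 | 0.651/0.582/0.504 | 0.564/0.521/0.465 |

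**Precision of a slope comparison.** Assume a linear trend, equal correlation r and k complete occasions at times t. The variance with free arm baseline means, divided by that with a common mean, is

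[Σt² − r(Σt)²/(1−r+kr)] / [Σt² − (Σt)²/k].

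Four occasions at days 0, 17, 32, 65 give Σt² = 5538 and (Σt)² = 12996, so the denominator is 5538 − 3249 = 2289. At r = .5 the numerator is 5538 − 0.2 × 12996 = 2938.8, ratio 1.28. At r = .6 and .7 the ratios are 1.20 and 1.14. With 16-25 occasions the range is 1.04-1.16. The loss is therefore 14-28% of variance with four occasions and 4-16% with many.

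**The baseline look.** With no effect and no time trend, a median split moves each half toward the mean by (1−r)√(2/π) SD: 0.40 SD at r = .5 and 0.24 SD at r = .7. On satisfaction with life, with the phase 1 SD of 6 (section 2.2), 0.40 SD is about 2.4 points each way. Simulated share of trials in which low and high halves differ at p < .05 (r .5-.7; pooled N 76-100, one arm 38-50):

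| What is compared | Pooled | PPJ arm only |
|---|---|---|
| Two-point change score | 79-99% | 48-85% |
| Slope, four occasions | about 62-94% | about 35-66% |
| Slope, 16-25 occasions | about 20-63% | about 12-36% |

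Separate runs differ by a few points (for example 34-70% in one arm with four occasions). As an arm-by-baseline interaction the rate is about 5%.

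**Group teaching.** If outcomes cluster by PPJ group in the treatment arm only, with m per group, the unadjusted variance is multiplied by [1 + 1 + (m−1)·ICC]/2. This is 1.10 at m = 5, ICC .05 and 1.45 at m = 10, ICC .10, so the standard error should be 5-20% larger. Simulated at 50 per arm, a nominal 5% t-test rejects 6-8% of the time at ICC .05 and 7-10% at .10. A baseline-adjusted test with no group term (r = .6) rejects about 7-9% and 9-14%, because adjustment shrinks the residual but not the group variance. With the group term the rate is 3-6%.

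**Sizing the next trial.** For an illustrative 0.4 SD at 80% power: 99 per arm unadjusted; 74, 63 or 51 adjusted at r = .5, .6 or .7; and 67-107 at r = .6 with ICC .02-.10 and groups of 5-10.

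**The case against.** Feasibility is the main aim, the mediators are secondary, and no decision rule uses these p-values. For mediators asked at every upload, the slope model loses only 4-16% of variance, about 2-8% of the standard error. The baseline look is an option offered as an example, and an arm-by-baseline reading is open. All of this stands and limits the weight of the point.

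Three stronger readings are tempting, and the documents do not support them:

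- *The arm comparisons are biased.* They are not. Under randomization the unadjusted comparison is unbiased; only precision is lost.
- *The baseline look would mainly show regression to the mean, with false-positive rates of 79-99%.* Those rates belong to a pooled two-point change score. The look in section 17.3 follows a sentence on multi-level change over time, and over 16-25 occasions the artefact is much diluted. In a PPJ-arm-only look at r of .7 or more, a real 0.5 SD low-high difference would match or exceed it.
- *The main model must carry a PPJ-group term.* The ICC and group sizes are unknown. Section 8.1 recruits controls in the same batches, so clustering may be by cohort and shared by both arms. In an approximate simulation of that case at ICC .05-.10, the plain t-test is slightly conservative (about 4-4.6%) and a treatment-arm-only term overstates the standard error by roughly 10-28%. Under one-arm clustering the group variance is estimated as zero in about 13-60% of simulated trials.

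**Conclusion.** The point holds as an improvement to consider, for the continuous mediators only; it does not touch the yes/no outcomes. At 50 per arm, the precision given up by a t-test is worth 0.08-0.16 SD in detectable difference against post scores (0.566 to 0.490-0.404) and 0.03-0.08 SD against change scores. For slopes it is moderate with four occasions and small with many.

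The baseline look, if pooled or confined to the PPJ arm, has a false-positive rate well above 5% on every schedule examined, highest for two-point and four-occasion measures. Whether it would be run that way is not stated.

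Clustering by PPJ group is a plausible further source of error whose size cannot be known from the documents.

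All figures rest on assumed r, ICC, group size, 1:1 allocation, survey days and complete data. Person-to-person variation in slope would lower the slope figures further.

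**What to change.** - (a) Replace the t-test on means with a comparison at a named time point, for example the end of Phase 2, adjusted for the baseline value of the same measure.
- (b) For rate of change, keep baseline as an outcome in the multi-level model with one common baseline mean for both arms. Arm-by-time then still answers the question in section 5.2.
- (c) Examine baseline level only as an arm-by-continuous-baseline interaction, labelled exploratory.
- (d) Keep PPJ-group membership in the analysis file. As a sensitivity analysis, report a model with a PPJ-group random effect in the treatment arm and small-sample degrees of freedom. State that the ICC is unknown and that clustering may instead follow the recruitment cohort in both arms.
- (e) Report the pre-post correlation among the statistics used to size the larger trial, and plan over a range of ICCs; the pilot's own estimate will be too unstable.

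The cost is analysis-plan wording and slightly more analysis work, with no new data. Intervals in the sensitivity analysis will be wider if outcomes cluster. At ICC .05-.10 and r = .6, adjusted standard errors grow about 8-31%, which gives back part of the gain. With five groups of 10 at ICC .05, power for a true 0.5 SD is about 67%, against about 70% for a plain t-test that ignores clustering.

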- 5.1. Study Design: This study is a randomized control trial with a one-month follow up. In this mixed-methods study we will collect quantitative and qualitative data. Questions related to feasibility and acceptability as well as hypothesized outcomes (increased treatment retention and decreased recurrence of substance use) and hypothesized mediators will be assessed quantitatively via self-report questionnaire instruments and participant treatment record, as described below. Qualitative data will focus on subjective experiences of PPJ and logistics of study implementation. The spoken words of participants during group and the written content of their journals also comprise qualitative data that we will study. This has been outlined for the participant in the informed consent document. Qualitative and quantitative data will be combined using integrative strategies recommended by Caracelli and Greene³⁹ and Li, Marquart, and Zercher.⁴⁰ In this integrative process, convergence across different data sources will be documented, and divergence will be examined further to elucidate deeper understandings.^{41,42} Who will administer these measures? The quantitative measures will be assessed via electronic Qualtrics survey that the research participants will access and complete themselves. (In the event there are technological difficulties, we might administer these surveys as paper questionnaires). At baseline, research staff will hand the participant the iPad (a computer can be used as back up) to complete the electronic Qualtrics survey. (For the electronic administration of this study, we will screen participants on Zoom and send them the link to the survey in the Zoom chat or via text or email, or we will provide them with the url.) During group, the research staff conducting the group will hand out the iPads and participants will use them to upload a picture of their journal entry and answer Qualtrics questions. (For the electronic administration of this study, we will send the link to the survey to participants electronically or give them the URL to navigate there themselves). Participants will use their own smart phones or tablets. Outside of group sessions, NUWAY Staff will make the iPads available for this same purpose (for electronic administration, we might retain a couple of iPads at the treatment center for clients to use

PROTOCOL TITLE: Journaling and Addiction Recovery

VERSION DATE: 13 April 2021

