We will use REDCap software to collect and organize study data including information collected on the screening check list, recruitment and enrollment and retention data, group attendance, study participation, exit interview, and follow up interview data. We will also obtain consent signatures electronically using REDCap.

Please note that the wording described in all participant-facing documents and questionnaires may be modified slightly to improve word choice or correct typos or other errors.

We will use Zoom features such as sharing our screen, white board, polls, and waiting room to enhance learning and protect integrity of group sessions.

We will teach basic Zoom skills (how to raise your hand, how to use the chat box, etc.).

5.

5.2. **Procedures.** This study will be advertised to be a study of “journaling in recovery from addiction.” All those interested in the study will be screened first by NUWAY staff to see if they meet basic criteria (see “prescreening guide for NUWAY staff,” attached) and then by research staff (using Zoom for electronic administration, see screening procedures, below). After screening and administration of the baseline assessment battery, individuals will be randomized into treatment and control groups using randomly generated pairs of numbers or using REDCap’s randomization procedure.

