7.1. Participants will be encouraged to email or call the PI in about a year's time to obtain study results in the form of academic posters or academic manuscripts or other products. Upon such requests, the PI will email or send via regular mail these products as well as an easy-to-understand fact sheet summarizing the results to date, to improve accessibility to study findings for lay readers. This opportunity is mentioned in the informed consent document. In general, the PI will share research findings at community-based, local, regional, and international conferences, during class or other lectures, and will publish study findings in academic journals. We will also make a presentation of findings to NUWAY staff when the study is over and throughout the study, as requested by NUWAY.

8. Study Duration

8.1.

- The duration for an individual participant's participation in the study is anticipated to be five to nine weeks as follows: Phase 1: 2.5 weeks, Phase 2: 2 weeks, a qualitative exit interview to take place as soon as possible at the 5 week mark, and a follow-up interview approximately 30 days after the exit interview.
- The duration anticipated to enroll all study participants: Enrollment will be rolling. We will recruit 10-20 individuals at a time to populate 1-2 treatment groups and corresponding individuals for the control groups. This study will last approximately 2 years. Typically, we will screen and consent and enroll participants during the week before groups start.
- The duration anticipated to complete all study procedures and data analysis: Including manuscript production and publication, approximately four years.

9. Study Population

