"We will not ask you about child or vulnerable adult abuse. If you tell us about child or vulnerable adult abuse or neglect, we may have to report it to authorities because of law or policy. This is true if you tell us in group, one on one meetings, or in journal entries. Also, if we learn (in person or in any other contact you have with us) that you are at risk for hurting yourself or others, we will inform NUWAY treatment staff of this information as soon as possible.

"In general, if something worries us about what you share with us in any way, we will let NUWAY staff know. This includes any time you tell us that you have used drugs or alcohol. Telling us that you have used drugs or alcohol will have the same consequences as if you told a NUWAY staff member that you used drugs or alcohol. NUWAY staff would work with you to make sure that you have the support you need to get back on track related to your recovery.

"If you tell us that you committed a crime, we would tell NUWAY Staff. Telling us that you committed a crime would have the same consequences as if you told a NUWAY staff member that you committed a crime. If you are on probation or parole, NUWAY staff would need to report this to your probation or parole officer.

"If you tell us that you intend to hurt yourself or someone else, we would tell NUWAY staff.

"Some of these things that you might tell us might have consequences related to your treatment status at NUWAY.

"In general, the NUWAY Staff will not find out your answers to the iPad surveys."

11. Number of Participants

11.1. Number of participants to be consented will be approximately 100.

12. Recruitment Methods

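### Section 5.2 plans to test the randomised arms for significant differences at baseline, where any difference among all those randomised is chance; describe baseline by arm without p-values instead

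*Combined protocol and SAP*

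**What the plan says.** The design is stated in section 5.1: "This study is a randomized control trial with a one-month follow up". Section 5.2 (*Procedures*) fixes the order of events: "After screening and administration of the baseline assessment battery, individuals will be randomized into treatment and control groups".

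In the Analysis Plan within section 5.2, the paragraph on techniques for comparing the arms concedes that the pilot is underpowered for differences between arms. It then says "we will compare differences between the treatment and control groups at baseline and over time using either t-tests or multi-level modeling" and adds "T-tests will reveal significant differences between groups". Multi-level models are given the other job, comparing rates of change.

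Section 17.1 refers back to this plan. Section 17.3 restates the arm comparison as t-tests on means and multi-level models on slopes. It uses baseline level only to form subgroups for change over time. The *Sample characteristics* paragraph in 5.2 describes baseline with means, SDs and percentages for study participants as a whole, not by arm. The only by-arm look at baseline that the plan names is therefore the tested one.

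Neither section gives a significance level, a list of variables or a multiplicity rule for the baseline tests, or says what follows from a significant or non-significant result. Neither names a baseline covariate for the between-arm comparison.

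**The concern.** A significance test asks whether an observed difference could be chance. For values recorded before a sound random allocation, the answer is known: among all those randomised, it is chance. The test is then unhelpful in both directions.

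- A small p-value says nothing about bias, yet it invites the reading that randomisation failed, or the choice of covariates after seeing the data.
- A large p-value does not show that the arms are alike. In a pilot of this size, a prognostically relevant imbalance can easily be non-significant.

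What matters for interpretation is the size of an imbalance and how strongly the measure predicts outcome. A p-value measures neither. Section 17.3 intends the descriptive statistics to feed sample-size work for a larger trial, so a clear by-arm description of baseline also has value beyond this pilot.

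**Working it through.** **Inputs from the documents**
- Sample size: section 11.1 says "Number of participants to be consented will be approximately 100". Section 17.2 says earlier data "was used to determine power for the original proposal with N=76".
- Allocation ratio: not stated. Section 8.1 says "We will recruit 10-20 individuals at a time to populate 1-2 treatment groups and corresponding individuals for the control groups", which suggests equal arms. I assume 1:1, giving 50 or 38 per arm.
- Significance level for baseline tests: not stated. Section 17.2 uses both one-tailed .10 and two-tailed .05. I take two-sided .05 as the main case.
- Number of variables: not stated. Table 2 marks 19 questionnaire rows at baseline. Counted by score, it gives HADS (2), SIP-AD, Commitment to Sobriety, gratitude, AA affiliation, social desirability, PANAS with serenity (3), self-efficacy, two cravings, happiness with recovery, life satisfaction, quality of life now and then (2) and flourishing. That is 18 scores, or 20 with age and years of education. Splitting demographics and subscales further gives about 30.

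**The plan's own figures.** The plan has none for the baseline comparison. Its power figures can be checked as a test of the equal-arms assumption. With 38 per arm, h = 2·arcsin√p1 − 2·arcsin√p2 and power = Φ(h·√(38/2) − z):
- abstinence, 41.5% v 24.8%: .609 (one-sided .10) and .344 (two-sided .05), against .61 and .34 stated ("for a 2-tailed test with $p < .05$, power would be .34");
- retention, 96.6% v 75.9%: .942 and .815, against .94 and .82 stated.

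All four reproduce, so 1:1 allocation fits the plan's own calculation.

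**Expected false signals, k × .05**

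| Variables tested | Expected false signals | Chance of at least one if independent, 1 − .95^k |
|---|---|---|
| 19 | 0.95 | 62% |
| 20 | 1.0 | 64% |
| 30 | 1.5 | 79% |

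Correlation between measures leaves the expected number unchanged but lowers the chance of at least one. In simulation with 20 measures and 50 per arm, that chance falls to a little over 50% at pairwise correlation .3 and a little over 40% at .5.

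**Largest imbalance that stays non-significant, t × √(2/n) in SD units**
- 50 per arm, two-sided .05: 1.984 × 0.200 = 0.397 SD.
- 38 per arm, two-sided .05: 1.993 × 0.229 = 0.457 SD.
- 50 per arm, one-sided .10: 1.290 × 0.200 = 0.258 SD.

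With 50 per arm the standard error of a standardised difference is 0.2. A chance imbalance above 0.2 SD therefore occurs in about 32% of variables, and above 0.3 SD in about 13%. Only 5% would be flagged at two-sided .05.

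**Carry-over to follow-up, a separate matter.** If a measure has baseline-to-follow-up correlation r (assumed; the documents give none), a baseline imbalance d shifts an unadjusted follow-up difference by r × d. With d = 0.39 SD, just under the threshold, the shift is 0.12, 0.20 or 0.27 SD for r = .3, .5 or .7. Given that imbalance, the type I error of the unadjusted t-test with 50 per arm is about 7.5%, 12% or 19% instead of 5%. This arises from the absence of baseline adjustment. It would be the same whether or not baseline was tested.

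**The case against.** The strongest reply is that the plan attaches no consequence to a baseline test. A reader might infer that non-significant imbalances will be accepted as no difference, or that covariates will be picked by baseline p-value. The documents say neither. Both are possible misuses, and the point must be put no higher than that.

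Second, the method is less definite than a battery of t-tests. Section 5.2 offers t-tests or multi-level models for baseline and follow-up together, and a baseline arm difference in a multi-level model is an intercept term. Section 17.3 speaks of means and slopes and names no baseline test. That is fair, but 5.2 includes baseline in the comparison, gives the search for significant differences to the t-test, and is not withdrawn elsewhere. A test of an arm-specific baseline intercept would be no more informative.

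Third, it is too strong to say that every baseline difference must be chance. Section 9.3 (items 15 and 16) foresees people declining once they hear their arm, and no analysis set is defined. In a set that drops such people, differences need not be chance alone. The statement holds for everyone randomised, and the fix is worded accordingly.

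Fourth, the figures rest on assumptions. The significance level, ratio and number of tests are not stated. Fifty per arm also treats all of about 100 consented as randomised, although section 9.3 (item 11) lets people eligible only for the waiting list sign the main consent. This stands, so the figures are given as conditional ranges.

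Fifth, a reader might attribute the follow-up shift of up to 0.27 SD to the baseline test. That would be wrong: deleting the test would not remove the shift. It also concerns t-tests on unadjusted follow-up scores, and the plan does not say whether raw or change scores are used. The slope comparison is not a raw follow-up comparison.

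**Conclusion.** The point holds as a minor fault in a stated analysis. For everyone randomised, the planned baseline comparison tests a null hypothesis that is true by design.

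Under two-sided .05, 1:1 allocation and about 20 variables, it would yield about one false signal (0.95 to 1.5 for 19 to 30 variables). Imbalances up to about 0.40 SD (50 per arm) or 0.46 SD (38 per arm) would go unflagged. At one-sided .10 with 50 per arm the threshold would be about 0.26 SD.

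The documents do not support saying that the plan will clear imbalances or select covariates on these p-values. Since the main objective is feasibility, acceptability and logistics, and the plan itself calls the arm comparisons underpowered, the change is desirable but not essential.

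**What to change.** 1. In section 5.2, delete *at baseline* from the tested comparison. Add that baseline means and SDs, or percentages, will be shown by arm for everyone randomised, including those who decline after hearing their assignment, with standardised differences and no p-values. Imbalance is then judged by its size and by the measure's relevance to outcome. The expected number of false baseline signals falls to zero.

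2. As a separate change in 5.2 and 17.3, state that each between-arm comparison of a measure collected at baseline adjusts for that measure's own baseline value, fixed in advance and whatever its baseline p-value. In a multi-level model this can be a baseline covariate or a common baseline mean for both arms. This adjustment, not the deletion, removes carry-over of a chance imbalance in that measure. Outcomes with no baseline value in Table 2, such as treatment satisfaction, retention and recurrence of use, are not covered by it.

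The cost is a sentence or two in each section. The first change reduces the analysis work, the second adds one term per model, and neither needs new data.
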